Patients scheduled for surgery will be randomized into two groups through simple open randomization. Randomization and data capture will be done using the REDCap system. Patients in group A, will receive a paravertebral block, administered preoperatively, which is standard of care. Those in group B will form a control group receiving no paravertebral block, which is standard of care. For the Paravertebral Block group; patients will receive an ultrasound guided paravertebral at the T7-10 levels bilaterally with 5 cc of .5% ropivacaine at each level. The ropivacaine is given as a local anesthetic. Intraoperative analgesic management will be at the discretion of the anesthesiologist. Currently receiving the block pre-procedure is standard of care and not receiving the block is standard of care and given based on physician assessment. For this study we would plan to randomize to obtain objective data for clinical decisions and improve patient outcomes between the two standard of care groups. Patients would normally be in one or the other group even if they do not participate in the study. With the randomization we hope to obtain more objective data regarding patient outcomes.

Following surgery patients in both groups, we will collect data from the first 48 hours after surgery and at discharge. Patients will not be required to come into the clinic for any extra visits, there will be no questionnaires.

Study design: Prospective, Randomized Trial

Subject Information

Target accrual is the proposed total number of subjects to be included in this study at Mayo Clinic. A "Subject" may include medical records, images, or specimens generated at Mayo Clinic and/or received from external sources.

Target accrual: 40

Subject population (children, adults, groups): Adults

Inclusion Criteria:

- Patients willing and have signed consent.
- Nonpregnant adults undergoing open pancreaticoduodenectomy via standard upper midline incision without contraindications to PVB

Exclusion Criteria:

- Not able or unwilling to sign consent.
- Currently pregnant or lactating.
- Patients with chronic pain, requiring daily opiate use at time of surgery.
- Patients intolerant of opiates, NSAIDS, acetaminophen or local anesthetics.

Biospecimens

Collection of blood samples. When multiple groups are involved copy and paste the appropriate section below for example repeat section b when drawing blood from children and adults with cancer.

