Power analyses may not be appropriate if this is a feasibility or pilot study, but end-point analysis plans are always appropriate even if only exploratory. Provide all information requested below, or provide justification if not including all of the information.

Power Statement:

The primary endpoint is postop pain visual analog scale. With pain scale ranging from 0 to 10, the standard deviation is estimated to be 2.5, based on two-sample t test, 20 patients per group (40 in total) will allow us to detect a mean difference of 2 points or larger in postop pain scale, with 0.05 significance level and 80% power.

Data Analysis Plan:

Patients demographic and baseline characteristics will be summarized as mean (SD) or median (range) for continuous variables and frequency (%) for categorical variables. Standardized mean difference will be calculated to indicate the size of the difference between the randomized groups. Postop outcome variables will be reported as mean (SD) or median (range) for continuous variables and frequency (%) for categorical variables. Two-sample t test will Wilcoxon rank sum test will be used to compare continuous variables between the two groups and chi-squared test or Fisher's exact test will be carried out to compare the categorical variables. All tests will be two-sided, with p value<0.05 considered statistically significant.

Endpoints

Primary:

Intra and postoperative pain medications consumption

Mean pain score initial 48 hrs postop

Length of stay

Return of bowel function

Secondary: Postop complications

References:

- Tempero, M.A., et al., *Pancreatic adenocarcinoma, version 2.2014: featured updates to the NCCN guidelines*. J Natl Compr Canc Netw, 2014. **12**(8): p. 1083-93.
2. Karim, S.A.M., et al., *The outcomes and complications of pancreaticoduodenectomy (Whipple procedure): Cross sectional study*. Int J Surg, 2018. **52**: p. 383-387.
3. Pawa, A., et al., *Paravertebral Blocks: Anatomical, Practical, and Future Concepts*. Current Anesthesiology Reports, 2019. **9**(3): p. 263-270.
4. Karmakar, Manoj K., *Thoracic Paravertebral Block*. Anesthesiology, 2001. **95**(3): p. 771-780.
5. Page, E.A. and K.L. Taylor, *Paravertebral block in paediatric abdominal surgery-a systematic review and meta-analysis of randomized trials*. Br J Anaesth, 2017. **118**(2): p. 159-166.
6. Novak-Janković, V. and J. Marković-Božić, *REGIONAL ANAESTHESIA IN THORACIC AND ABDOMINAL SURGERY*. Acta Clin Croat, 2019. **58**(Suppl 1): p. 96-100.

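### Does the 48-hour mean pain score need stated assessment times and an averaging rule before it can be analysed fairly?

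*Combined protocol and SAP*

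**What the plan says.** The Endpoints section names "Mean pain score initial 48 hrs postop" as one of four primary endpoints. The Power Statement is built on pain alone: "The primary endpoint is postop pain visual analog scale". It takes an SD of 2.5 on a 0 to 10 scale and says that 20 patients per group "will allow us to detect a mean difference of 2 points or larger in postop pain scale".

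The Methods text under Study Design and Methods says that, in both groups, "we will collect data from the first 48 hours after surgery and at discharge". It adds that "there will be no questionnaires". Patients are "randomized into two groups through simple open randomization", and "Randomization and data capture will be done using the REDCap system". The Data Analysis Plan states: "Two-sample t test will Wilcoxon rank sum test will be used to compare continuous variables between the two groups". Either test needs one number per patient.

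The document does not say when pain is scored within the 48 hours, how often, or how a patient's scores are combined beyond the word mean.

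**The concern.** Without questionnaires or a scoring schedule, the pain scores probably come from routine charting. This is an inference, since the document names no source. Routine charting may be denser soon after surgery. An ordinary mean gives each score the same weight, so a densely charted period counts for more than its share of the 48 hours.

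Two consequences could follow.

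- **A different estimand.** The block is given once, before surgery, so its effect may change over the window. The charting pattern would then partly decide which average effect is estimated, even if both arms are charted alike.
- **A false difference.** Allocation is open. If staff charted one arm more densely than the other, two arms with identical pain could have different means.

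An unwritten rule could also be chosen after the data are seen. For a primary endpoint on which the sample size rests, these are fair questions.

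**Working it through.** **The plan's own figure.** Inputs from the Power Statement: difference 2, SD 2.5, 20 per group, alpha 0.05, power 80%. The Data Analysis Plan makes all tests two-sided. The standardized difference is 2/2.5 = 0.8. A two-sided t test then needs 26 per group (25.5 before rounding), and 20 per group gives 69.3% power. A one-sided test at 0.05 gives 79.9%, which matches the stated figure. That mismatch is a separate matter and nothing below depends on it.

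**How far charting can move a mean.** Assume pain of 7 over 0–6 h, 5 over 6–24 h and 3 over 24–48 h.

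- Hour-weighted mean: (7×6 + 5×18 + 3×24)/48 = 204/48 = 4.25.
- Even 4-hourly charting (on average 1.5, 4.5 and 6 scores per period): (10.5 + 22.5 + 18)/12 = 4.25.
- Hourly for 6 h, then 4-hourly (6, 4.5 and 6): (42 + 22.5 + 18)/16.5 = 5.00.
- Twelve scores in the first 6 h, then 4-hourly (12, 4.5 and 6): (84 + 22.5 + 18)/22.5 = 5.53.

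The level moves by 0.75 to 1.28 points. If both arms share the pattern and there is no effect, both move equally and the difference stays at zero.

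**What a false difference requires.** Assume no effect and pain falling in a straight line from 6 to 3, so the true mean is 4.50. Charting was simulated with random start times for three patterns: 4-hourly throughout; six hourly scores, then 4-hourly; eight 15-minute scores, then 4-hourly.

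| Pattern | Plain mean | Fixed-interval mean |
|---|---|---|
| 4-hourly | 4.50 | 4.50 |
| Hourly first | 4.85 | 4.53 |
| 15-minute first | 5.03 | 4.51 |

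The fixed-interval mean takes one score from each of twelve 4-hour intervals, the one nearest the midpoint, and weights them equally. If one arm is 4-hourly and the other is dense early on, the plain mean gives false differences of 0.35 and 0.53, and the fixed-interval mean gives 0.03 and 0.01.

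For the false-positive rate, the noncentrality is d/(2.5×√(2/20)) = d/0.791 with 38 degrees of freedom. For d = 0.35 it is 0.443 and the two-sided rate is 7.2%. For d = 0.53 it is 0.670 and the rate is 10.0%. Both use the plan's SD of 2.5. The plan does not say whether that SD is for a single score or a 48-hour average, and a smaller SD would raise these rates.

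**Shared charting with a changing effect.** Assume a 3-point effect. If it lasts 12 h, the hour-weighted value is 3×12/48 = 0.75, and the plain mean under the two front-loaded patterns gives 1.30 and 1.57. If it lasts 24 h, the hour-weighted value is 1.50 and the plain mean gives 1.87 and 2.05. If it is constant, every rule gives 3.00. Under even 4-hourly charting the plain mean is within about 1% of the hour-weighted value.

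**Whether another rule is clearly better.**

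- Shifted 4-hourly grids (1, 5, …, 45 h against 3, 7, …, 47 h) give 4.5625 and 4.4375. The false difference is 0.125 by the plain mean and by the fixed-interval mean.
- If one arm has a repeat score an hour after any score of 6 or more, the plain mean gives +0.07 and the fixed-interval mean −0.06.
- If one arm has extra scores recorded only when pain is 6 or more, the figures are 0.32 and 0.13.
- A time-weighted mean with the end scores carried out to 0 and 48 h gives about 4.50 for all three patterns in the table. Cut at the first and last score instead, it can shrink a 4-hour effect to 0.55 of its size.

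The preferred rule therefore depends on the charting pattern, which the document does not describe.

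**The case for a change.** The strongest case for a change is that the gap is real and cheap to close. The pain endpoint carries the sample size, the tests need one value per patient, and no derivation is written down. Open allocation leaves room for charting to differ by arm, and an unwritten rule leaves room for choice after the data are seen. A few lines of text and a time stamp in REDCap would settle it.

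Much of this stands. The times and the derivation are absent, nothing was blacked out there, and the arithmetic on dense charting is correct.

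The inference to harm does not stand. The Methods text describes the same 48-hour data collection for both groups and no arm-specific monitoring. The false differences of 0.35 and 0.53 need every patient in one arm to be charted hourly or every 15 minutes just after surgery while every patient in the other is charted 4-hourly from the start. The latitude is also narrow, because window and summary are both fixed and the natural reading is each patient's mean of recorded scores. Departing from that would need a reason. Writing a different rule into the plan would replace one defensible weighting with another that is open to the same kind of argument.

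**Conclusion.** No change follows. The endpoint has a window (0–48 h) and a summary (the mean). An analyst would compute each patient's mean of recorded scores in the same way in both arms, which supplies the single value that the t or Wilcoxon test needs. With shared charting this gives a fair comparison. If the effect varies over time and charting is dense early, the mean leans towards the early hours. That changes the average being described but creates no difference where none exists.

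The possible harm is conditional. It is zero with shared charting and a constant effect, and about 1% of the estimate with even 4-hourly charting. It reaches 0.35 to 0.53 points, or a false-positive rate of 7.2% to 10.0% at an SD of 2.5, only when charting differs sharply by arm. Every charting pattern, pain course and effect duration behind these figures is an assumption, and the document fixes neither size nor direction. No alternative weighting is better in all the cases examined. This is a gap in detail that competent analysis fills, not a defect in the design.

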IRB Minimal Risk Protocol Template

Note: If this study establishes a human specimen repository (biobank) for research purposes, do not use this template. Use the Mayo Clinic Human Specimen Repository Protocol Template found on the IRB home page under Forms and Procedures at <http://intranet.mayo.edu/charlie/irb/>

First-time Use: Use this template to describe your study for a new IRB submission.

1. Complete the questions that apply to your study.
2. Save an electronic copy of this protocol for future revisions.
3. When completing your IRBe application, you will be asked to upload this document to the protocol section.

Modification: To modify this document after your study has been approved:

1. Open your study in IRBe. Click on the study 'Documents' tab and select the most recent version of the protocol. Save it to your files.
2. Open the saved document and activate "Track Changes".
3. Revise the protocol template to reflect the modification points , save the template to your files
4. Create an IRBe Modification for the study and upload the revised protocol template.

General Study Information

Principal Investigator: [name]

Co-investigators: [name], [name]

Study Title: Paravertebral block vs no block in open pancreaticoduodenectomy: prospective randomized controlled trial
NCT05820997

Protocol version number and date: V1 11/2/2022, V3 1/17/2023

Research Question and Aims

Hypothesis: We hypothesize that patients undergoing open pancreaticoduodenectomy who receive a paravertebral block, will have less postoperative pain and a shorter length of stay than those who only receive no paravertebral block.

Aims, purpose, or objectives:

Compare intra and postoperative pain control between Paravertebral block vs no block in open pancreaticoduodenectomy. Length of stay, and complications will also be recorded.

Background (Include relevant experience, gaps in current knowledge, preliminary data, etc.):

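### The only safety endpoint is worded as postoperative although the block is given before surgery, so transient harms of block placement may go uncounted

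*Combined protocol and SAP*

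**What the plan says.** Four parts of the combined protocol and SAP bear on this point.

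- **Study Design and Methods, timing and arms.** "Patients in group A, will receive a paravertebral block, administered preoperatively". The injection is "ultrasound guided paravertebral at the T7-10 levels bilaterally". For the comparator, "Those in group B will form a control group receiving no paravertebral block"; no sham procedure is described.
- **Study Design and Methods, data collection.** For the period after surgery, "we will collect data from the first 48 hours after surgery and at discharge".
- **Research Question and Aims.** "Length of stay, and complications will also be recorded", with no restriction to the postoperative period.
- **Endpoints.** The only harm endpoint is "Secondary: Postop complications". It has no definition, event list, grading scale or time window. One of the primary endpoints in the same list is "Intra and postoperative pain medications consumption".

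For outcomes, the Data Analysis Plan speaks only of postoperative variables. The documents give no expected rate for complications or for harms of the block.

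**The concern.** The intervention under test is delivered before the period that the safety endpoint names. Harms of the procedure itself, from needle placement or from the injected local anesthetic, can begin as soon as the block is placed. An abstractor who follows the endpoint list literally would have no instruction to count an event that began at placement and was over by the end of surgery.

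Group B has no procedure, so this kind of event can occur only in patients who are blocked. Leaving it out can only remove events from that side of the comparison. Allocation is open, so staff who know the arm would be the ones deciding whether an early event belongs under an undefined term. The protocol says the trial is meant to inform the choice between two accepted options, and that choice needs the procedure's own harms as well as its benefit.

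**Working it through.** **Step 1. Set the sections side by side.**

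| Section | Period covered | Harms named? |
|---|---|---|
| Aims | Not restricted | Complications, unqualified |
| Methods, block | Before surgery, group A only | No |
| Methods, collection | After surgery: first 48 hours, then discharge | Not itemized |
| Endpoints, primary | Analgesic use: during and after surgery | No |
| Endpoints, secondary | After surgery | Complications |
| Data Analysis Plan | Postoperative outcomes | Not itemized |

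The endpoint list names the intraoperative period for analgesic use and does not name it for complications. Read as written, the complication count therefore starts after surgery. The aims permit a wider reading, but nothing carries it into the endpoint or the analysis.

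**Step 2. What can be lost.** A block-procedure harm is lost only if it (a) occurs, (b) resolves before surgery ends, and (c) is read as not postoperative. A harm that persists, or is first detected after surgery, can still be counted.

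**Step 3. Size, by assumption.** The plan gives no figure for complications, so there is none to reproduce. The one input from the documents is 20 patients per group (Power Statement), which was set for pain. Simple randomization may not give exactly 20.

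Let r be the assumed per-patient rate of any block-procedure harm and f the assumed share that resolves before surgery ends. The expected number lost is 20 × r × f, and the chance of losing at least one is 1 − (1 − r × f)^20.

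| r | f = 1: expected lost | f = 1: chance of ≥1 | f = 0.5: expected lost | f = 0.5: chance of ≥1 |
|---|---|---|---|---|
| 1% | 0.2 | 1 − 0.99^20 = 18.2% | 0.1 | 1 − 0.995^20 = 9.5% |
| 2% | 0.4 | 1 − 0.98^20 = 33.2% | 0.2 | 1 − 0.99^20 = 18.2% |
| 5% | 1.0 | 1 − 0.95^20 = 64.2% | 0.5 | 1 − 0.975^20 = 39.7% |

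The f = 1 column is the upper bound at each rate: it is the chance of any block-procedure harm at all. If f is 0, nothing is lost.

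**Step 4. What counting these events could show.**

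- With no event in 20 blocked patients, the one-sided 95% upper limit is 1 − 0.05^(1/20) = 13.9%.
- Against 0/20 in group B, the two-sided Fisher p-value for k events in group A is 2 × C(20,k)/C(40,k).
  - k = 4: 2 × 4,845/91,390 = 0.106.
  - k = 5: 2 × 15,504/658,008 = 0.047.

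Five block-arm events against none would be needed to reach p < 0.05.

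**The case against.** The strongest reply is that the gap is one of wording. The aims promise that complications will be recorded, without qualification, and a site guided by that line would record an event at block placement. The collection sentence describes the postoperative phase and cannot be the full list of what is collected: the plan also calls for baseline characteristics and intraoperative analgesic use. An undefined complication term can also take in harms that persist or come to light later; a pneumothorax found after surgery is an example. Finally, complications are secondary, safety is not part of the hypothesis, and one or two extra events would not change a test that needs five against none.

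Much of this stands. It means the loss is possible rather than certain and is confined to transient events. It does not close the gap, because the endpoint list is the natural basis for abstraction and analysis, and it conflicts with the aims. The low power argues for descriptive reporting; it does not justify leaving the events out.

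A reader might infer that the safety comparison favours the block. The documents do not support that. The bias depends on such events occurring, resolving early and being left out, and no rate is given. The direction is fixed only for harms of the procedure itself. Other intraoperative events, hypotension among them, can occur in either arm and would go uncounted in both.

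**Conclusion.** The point holds in a limited form. As worded under Endpoints, the only safety endpoint begins after the tested intervention has been given, and it does not match the unqualified wording of the aims. Harms of block placement or local anesthetic injection that arise and resolve before the end of surgery may go uncounted, which could understate harm in the block arm.

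The size is unknown. The 10% to 64% range rests on assumed harm rates of 1% to 5%, an assumed resolving share of one half to one, 20 blocked patients, and a literal reading of the endpoint. A reader might take 18%, 33% and 64% as the chances that an event is missed at rates of 1%, 2% and 5%. They are chances of any block-procedure event, and they equal the chance of a loss only if every such event resolves before surgery ends.

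The pain comparison is unaffected. Counting these events would make them visible, but 20 per group cannot give a powered safety comparison.

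**What to change.** Reconcile the aims, Methods and Endpoints as follows.

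- Change the secondary endpoint to *perioperative complications*, counted from one common start point in both arms, for example arrival in the preoperative area, to discharge. The start must precede the block and be the same for both groups; starting at the block in group A and at arrival in group B would give the arms unequal windows.
- List block-procedure events separately, for example vascular or pleural puncture, pneumothorax and local anesthetic toxicity, taken from the procedure note and the anesthesia record.
- Report these events descriptively, as counts with exact confidence intervals.
- Keep abandoned blocks, and group B patients who received a block, out of this endpoint. They are adherence items.

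The cost is a revised endpoint line, matching wording in the other sections, and a few REDCap fields filled from existing records. No added visit or change of treatment is needed. The downside is a little more chart abstraction and possibly a less favourable count in the block arm.
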